15.0 Statistical Appendix

This appendix provides further details related to the treatment of missing data for the primary and sensitivity analyses of the primary endpoint.

For multiple imputations and other instances where random seeds are required, the values used (in order) are:

8392857
2985729
1843255
9086284
5547484
8017456
9597295
2252256
4821871
9852467
5126715
3232132
9841654
3645284
1587345

Note that not all seeds may be required in programming the multiple imputations. If additional seeds are needed, they will be chosen by adding 1 to each of the values above, again using them in order.

The number of imputations for the multiple imputations will be 20.

For the primary analysis, a multi-stage process will be applied:

Stage 1: Subjects will have their 11-point NRS scores imputed. First, using all visits, intermittent missing data will be imputed using the Markov Chain Monte Carlo (MCMC) method implemented with the SAS MI procedure; data imputed following subject discontinuation via this process will be censored out of the resulting dataset so that only intermittent missing data is imputed via this method. Second, monotone missing data will be imputed following subject discontinuation using SAS proc MI. For each stage, MI will be performed within treatment group with covariates for baseline NRS score, use of prior anti-itch medication, and presence of select medical conditions. Should convergence issues occur due to small cell size for the one or both of the categorical covariates at either stage, the appropriate covariate(s) will be removed from the model.

Stage 2: Using the resulting complete datasets, the change from baseline with respect to the 11-point NRS will be calculated; patients will be categorized as responder if they have a 3-point (or greater) improvement over baseline. Week 12 values will serve as the primary timepoint. The 20 MI runs will be analyzed independently using a logistic

model and the results combined using SAS proc MIANALYZE. Logistic model covariates will include treatment, baseline NRS score, use of prior anti-itch medication, and presence of select medical conditions. As with the MI, should convergence issues occur due to small cell sizes, the appropriate categorical covariate(s) will be dropped as necessary.

Should a sample size increase occur, the above process will be implemented completely independently among subjects contributing the interim results and those following the interim analysis.

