8.2.2 Primary Efficacy Analysis

In the primary efficacy analysis, missing NRS data at the end of Week 12 will be imputed using a multiple imputation (MI) approach, assuming that subjects who discontinue double-blind treatment early would have similar Worst Itching Intensity NRS scores as other subjects in their respective treatment arm who have complete data:

- Intermittent missing NRS scores will first be imputed using the Markov Chain Monte Carlo (MCMC) method implemented with the SAS MI procedure, which is appropriate for non-monotonic missing data.
- The monotone missing NRS values will then be multiply imputed with the SAS MI procedure using the monotone regression method.

- For each stage, MI will be performed within treatment group with covariates for baseline NRS score, both randomization stratification factors, and the non-missing NRS scores for each week. Should convergence issues occur due to small cell size for the categorical covariates at either stage, those covariates will be removed from the model.
- The proportion of subjects who have an improvement from baseline with respect to the weekly mean of the daily 24-hour Worst Itching Intensity NRS score ≥ 3 points will be calculated for each imputed dataset. Differences between CR845 0.5 mcg/kg and placebo with respect to the primary endpoint will be compared using a logistic regression model containing terms for treatment group, baseline NRS score, use of anti-itch medication during the week prior to randomization, and presence of specific medical conditions.
- Twenty imputations will be performed.
- Results of the logistic regression on the multiply imputed data sets will be summarized by the SAS MIANALYZE procedure.

The observed number and proportion of subjects with ≥ 3 -point improvement among the non-imputed data will be reported along with the imputed data logistic regression model-based estimates of the proportions of responders, odds ratio, 95% confidence intervals (CIs), and p-value.

Sample size adjustment

The above MI process will be implemented completely independently among subjects contributing the interim results and those following the interim analysis. Likewise, the logistic regression and results described above will be generated independently for both samples, with the samples combined and adjusted as follows:

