The final p-value will be calculated using the Cui, Hung, Wang (CHW) procedure where the z-score is a weighted average of the z-score at the interim and the z-score observed for data collected after the interim, following the formula below:

$$Z_{CHW} = Z_{interim} * \sqrt{(n/N)} + Z_{post-interim} * \sqrt{(1 - n/N)}$$

where n is the number of randomized subjects at the interim and N is the initial number of subjects planned (350).

The adjusted odds ratio estimate prior to exponentiating and the 95% CI will be obtained using methodology suggested by Hung and Lawrence:

$$\hat{\delta} = \frac{r_1 \hat{\delta}^{(1)} + \sqrt{1 - r_1} \sqrt{N^* - r_1} \hat{\delta}^{(2)}}{r_1 + \sqrt{1 - r_1} \sqrt{N^* - r_1}}$$

where

$r_1 = n/350$

$N^* = (\text{Re-estimated total sample size})/350$

$\hat{\delta}^{(1)}$ = Least square mean difference from stage 1 analysis

$\hat{\delta}^{(2)}$ = Least square mean difference from stage 2 analysis

$$95\% \text{ CI} = \hat{\delta} \pm \left(\frac{\hat{\delta}}{Z_{CHW}} * 1.96 \right)$$

Note that it is possible for Z_{CHW} and δ to have opposite directions, particularly when close to zero, in which case the absolute value of the ratio will be used in the above formula.

See Section [11](#) for further details on the interim analysis.

The primary analysis and each sensitivity analysis will also be performed using the full combined dataset with the missing data imputed separately for interim subjects and post-interim subjects. No CHW adjustment will be conducted. Presentation of results will start with these analyses (additionally including the CHW results) and then follow with the results of the analysis from each individual stage.

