8.2.4.3 Key Secondary Analyses

5-D Itch Scale and the Skindex-10 Scale

The 5-D Itch Scale and the Skindex-10 Scale scores will be analyzed only at Week 12 using an analysis of covariance (ANCOVA). The model will contain treatment as fixed effects, with baseline score and the randomization stratification variables as covariates. The baseline 5-D total score and the Skindex-10 total score will be defined as the value collected on Day 1, prior to randomization. This is a change from the final protocol dated 21DEC2017 and is being implemented to address the FDA advice received on 10JAN2019 stating that “*the analysis [of continuous efficacy endpoints] should be based on only data from one timepoint (e.g. Week 12); however, modeling approaches using all timepoints may be used as supportive analyses.*”

Additionally, subjects who discontinue treatment but continue on study and have 5-D and Skindex-10 scores recorded will have these scores censored following discontinuation of treatment; missing data rules will apply to these censored values as though they had missing values/ dropped out from the study entirely.

For each domain in each questionnaire, missing values at Week 12 will be imputed using an MI approach, assuming that subjects who discontinue double-blind treatment early would have similar 5-D Itch and Skindex-10 scores as other subjects in their respective treatment arm that have complete data. All available visits will be included in the MI to

better inform the Week 12 imputed results. The MI approach will proceed as follows, using all ITT subjects (that is, it will not be split into IA subjects and post- IA subjects):

- Intermittent missing scores will first be imputed using the Markov Chain Monte Carlo (MCMC) method implemented with the SAS MI procedure, which is appropriate for non-monotonic missing data.
- The monotone missing values will then be multiply imputed with the SAS MI procedure using the monotone regression method.
- For each stage, MI will be performed within treatment group with covariates for baseline score, both randomization stratification factors, and all non-missing visit scores for each domain of the questionnaire. Should convergence issues occur due to small cell size for the categorical covariates at either stage, they will be removed from the model.
- Twenty imputations will be performed for each domain.

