14. SAMPLE SAS CODE

Below is the SAS code used to create the dataset to be used in the primary analysis. Weekly NRS scores will be subset on the ITT Population and the dataset will be transposed to create one observation per subject with separate variables for baseline (v1) through week 12 (v13) values. These values as well as a numeric variable for the planned treatment group (trt01pn) and numeric flags for anti-itch medication use at baseline (antiIn) and specific medical conditions (specmedn) will be used during the imputation procedures.

The first stage of imputation will create monotone missing data using MCMC and the following code:

```
proc mi data=INDATA seed=8392857 nimpute=20 MAXIMUM=10 MINIMUM=0
out=OUTDATA1 minmaxiter=1000000 ;
mcmc chain=multiple initial = EM(CONVERGE=0.001 maxiter=100000) NBITER=500
NITER=100 impute = monotone displayinit ;
var antiIn specmedn v1 v2 v3 v4 v5 v6 v7 v8 v9 v10 v11 v12 v13;
by trt01pn;
run;
```

Using the output data, imputed data following the last non-missing will be reset to missing so that only intermittent values are imputed in this first pass.

The second stage will use this output, then fill in the monotone missing values with the following MI code:

```
proc mi data=OUTDATA1 seed=2985729 nimpute=1 MAXIMUM=10 MINIMUM=0
out=OUTDATA2 minmaxiter=1000000 ;
monotone reg;
var antiIn specmedn v1 v2 v3 v4 v5 v6 v7 v8 v9 v10 v11 v12 v13;
by trt01pn;
run;
```

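### The SAP requires the primary imputation to be run separately in interim and post-interim subjects, but the SAS code it prints for the primary dataset pools the two stages

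*SAP*

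**What the plan says.** **SAP 8.2.2, sample size adjustment.** "The above MI process will be implemented completely independently among subjects contributing the interim results and those following the interim analysis". The models follow the same split: "the logistic regression and results described above will be generated independently for both samples". The two z-scores are then combined with CHW weights based on a planned N of 350. The analysis of the combined data without CHW adjustment is also to be done "with the missing data imputed separately for interim subjects and post-interim subjects".

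**SAP 14, sample code.** The section opens: "Below is the SAS code used to create the dataset to be used in the primary analysis". Its input is described so: "Weekly NRS scores will be subset on the ITT Population and the dataset will be transposed to create one observation per subject". Both PROC MI calls list the same variables, "var antiIn specmedn v1 v2 v3 v4 v5 v6 v7 v8 v9 v10 v11 v12 v13", and both have `by trt01pn` as the only grouping. There is no stage variable, no stage filter and no instruction to repeat the calls by stage.

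**SAP 8.2.4.3, 5-D Itch and Skindex-10.** The imputation here is deliberately pooled: "it will not be split into IA subjects and post- IA subjects".

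**Protocol 15.0.** The split is conditional: "Should a sample size increase occur, the above process will be implemented completely independently among subjects contributing the interim results". SAP 8.2.2 has no such condition, and SAP 12 does not list the difference.

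**The concern.** The method text and the printed code give two different computations of the primary p-value. SAP primacy, stated in SAP 1 and Protocol 8.1, settles SAP against protocol. It cannot settle one section of the SAP against another.

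The difference bears on the CHW test. Referring the weighted sum to a standard normal relies on the two stage z-scores being independent under the null hypothesis. With pooled imputation, a stage 1 dropout is filled in from a regression fitted partly on stage 2 subjects, and the reverse, so the stages share information. The stage 1 z-score in the final analysis is then also no longer a function of stage 1 data alone, although the sample size decision was taken on stage 1 data alone.

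SAP 8.2.4.3 analyses the ≥4-point secondary endpoint on the same dataset by the same method, so it is affected in the same way. SAP 8.2.3 also presents results before and after the interim separately, to judge the effect of the interim analysis. Pooled imputation would blur that comparison.

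**Working it through.** **Planning figures first.** The point disputes no printed number. For 30% placebo response, a continuity-corrected chi-square test at two-sided 5% and 90% power, the sample sizes per arm reproduce exactly as 134, 164, 204, 230 and 262. Power at 175 per arm comes out at 96.3%, 92.0%, 84.8% and 79.9%, against the printed 96%, 92%, 84% and 79%.

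**CHW weights.** With the interim at about half of 350 (SAP 11.1), n = 175 and N = 350, so each weight is √(175/350) = 0.707.

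**What correlation does.** Let the stage z-scores have standard deviations s₁ and s₂ and correlation r. Then

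Var(Z_CHW) = 0.5·s₁² + 0.5·s₂² + r·s₁·s₂.

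The test assumes s₁ = s₂ = 1 and r = 0, which gives variance 1.

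**Simulation under no effect.** From the SAP: 20 imputations within arm, responder cut at 3 points, Rubin's rules within each stage, CHW with equal weights. Assumed, because the documents give no values: 10%, 20% or 30% missing at Week 12, completely at random; within-patient correlation 0.3 or 0.7; one intermediate score; and an unadjusted log odds ratio in place of the covariate-adjusted logistic model. Stage sizes per arm were 88 + 87 (total 350) or 88 + 162 (total 500), with 6,000 trials per setting.

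| Missing | Correlation, split | Correlation, pooled | Type I error, split | Type I error, pooled |
|---|---|---|---|---|
| 10% | -0.004 to 0.012 | 0.038 to 0.085 | 3.9% to 4.2% | 4.2% to 4.5% |
| 20% | -0.008 to 0.008 | 0.080 to 0.139 | 3.5% to 3.9% | 3.7% to 4.2% |
| 30% | -0.014 to 0.009 | 0.131 to 0.241 | 3.0% to 3.5% | 3.0% to 3.7% |

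The largest rise in any one setting was from 3.45% to 4.20%, or 0.75 points (20% missing, within-patient correlation 0.3, 88 + 162 per arm). The Monte Carlo standard error of one rate near 4% is √(0.04 × 0.96/6000) = 0.25 points.

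**Why the error rate stays below 5%.** Take the setting with the largest correlation (30% missing, 88 + 87 per arm): s₁ = 0.840, s₂ = 0.853, r = 0.241.

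Var = 0.5 × 0.706 + 0.5 × 0.728 + 0.241 × 0.840 × 0.853 = 0.717 + 0.173 = 0.889, so the SD is 0.943.

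This matches the simulated SD of 0.943. The stage z-scores vary less than a standard normal because the Rubin variances are conservative here, and that outweighs the covariance term.

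**With a sample size increase.** A second run (10,000 trials per setting) assumed that stage 2 grows to 162 per arm when the absolute interim z-score lies between 0.5 and 2.0. This rule is an assumption. Correlation was -0.015 to 0.012 split and 0.047 to 0.228 pooled. Type I error was 3.5% to 4.2% split and 3.7% to 4.2% pooled. Pooling moved the final stage 1 z-score from its interim-only value by 0.09 to 0.20 on average.

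**A fuller model.** A separate simulation with 12 weekly scores, the stratification covariates, the logistic model and 20% monotone dropout (4,000 trials) gave a correlation of 0.02 split and 0.08 pooled, with rejection of 3.7% and 4.0%. The direction agrees.

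**The case against.** The strongest reply is that the governing rule is already explicit. SAP 8.2.2 states the split twice, and SAP 8.2.4.3 names the imputation that is not split, so the authors considered the question. SAP 14 is headed as sample code with a generic `INDATA`, and a programmer could meet 8.2.2 by running the same calls on each stage's subset. So it cannot be said that the trial will pool the stages. What remains is that the section presents itself as the code for the primary dataset, names the whole ITT Population as input, and fixes one seed per call. Nothing says which seeds a second run would take.

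Four stronger readings are tempting, and none is supported.

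- **Alpha inflation.** With unit-variance z-scores, r = 0.24 would give Z_CHW an SD of √1.24 = 1.114 and a two-sided error of about 7.8%. The stage z-scores do not have unit variance here, and no simulated setting exceeded 4.5%.
- **Changed verdicts.** One could count how often significance differs between the two rules. In a simulation at about 64% power, rerunning the same split rule with new random draws changed the verdict in 4.7% of trials, against 5.2% to 5.4% for split versus pooled. Most of the disagreement is imputation noise.
- **All NRS cut-points.** SAP 8.2.5.1 reuses the dataset for the other thresholds but applies no interim adjustment, so the correlation of the stage z-scores does not matter for them.
- **A third live rule in the protocol.** The condition in Protocol 15.0 yields to the SAP.

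**Conclusion.** The point holds as a contradiction inside the SAP on how the primary p-value is computed. Run as printed, the code breaks the SAP's own rule and the independence that the CHW combination relies on. The primary endpoint and the ≥4-point secondary endpoint are affected.

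The effect is small: a correlation of about 0.04 to 0.24 in place of about 0, a mean shift of 0.09 to 0.20 in the stage 1 z-score under the assumed increase rule, and at most about 0.8 points on a type I error that stayed below 5%. These sizes rest on the assumed missing rates, within-patient correlations and increase rule, and they grow with the amount of missing data. The textual conflict depends on none of them. It should be corrected before database lock, but it does not by itself put the validity of the trial in doubt.

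**What to change.** In SAP 14, either:

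1. add a numeric interim/post-interim flag to `INDATA`, sort by it, and put it with `trt01pn` in the BY statement of both PROC MI calls; or
2. state that the code is run separately on the interim and post-interim subsets, and assign seeds to each run.

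Under either option, the second call also needs `_Imputation_` in its BY statement. As printed, it reads the 20 stacked copies with `nimpute=1` and no such variable. That is a separate defect, which adding a stage flag alone would not repair, but the same edit can cover it.

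Add one line to SAP 12 recording that the split now applies whether or not the sample size is increased, unlike Protocol 15.0. No protocol amendment is needed, because the SAP has primacy.

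The cost is one derived variable, two edited BY statements and one sentence. No new data are needed.

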The proportion of subjects achieving ≥ 4 -point improvement from baseline with respect to the weekly mean of the daily 24-hour Worst Itching Intensity NRS at Week 12 of the Double-blind Treatment Period will be analyzed following a methodology identical to the one employed for the primary analysis of the primary endpoint (see section 8.2.2). The same dataset will be utilized; separate flags for various cut points of improvement will be utilized to facilitate these analyses. The analysis will be completed for both the ITT and PP Populations.

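### The stage 2 PROC MI call in SAP 14 leaves `_Imputation_` out of its BY statement, so the printed code draws the regression parameters once per arm instead of twenty times

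*SAP*

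**What the plan says.** SAP 8.2.2 describes the primary analysis in two imputation stages: MCMC for intermittent gaps, then monotone regression for what remains missing. On grouping it says "For each stage, MI will be performed within treatment group with covariates for baseline NRS score, both randomization stratification factors", and on number, "Twenty imputations will be performed". On combination it says "Results of the logistic regression on the multiply imputed data sets will be summarized by the SAS MIANALYZE procedure". Section 15.0 of the protocol agrees: "The 20 MI runs will be analyzed independently using a logistic" model, with the results then combined.

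SAP 14 prints the program and introduces it with "Below is the SAS code used to create the dataset to be used in the primary analysis". Stage 1 is "proc mi data=INDATA seed=8392857 nimpute=20 MAXIMUM=10 MINIMUM=0", run by treatment. The only step described before stage 2 resets values after each subject's last observed score to missing. Stage 2 is "proc mi data=OUTDATA1 seed=2985729 nimpute=1 MAXIMUM=10 MINIMUM=0", again with `by trt01pn;` alone. Neither the code nor the surrounding text has a loop, a split or a BY variable for imputation number.

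For the secondary endpoint of at least 4 points' improvement, SAP 8.2.4.3 says "The same dataset will be utilized".

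**The concern.** Setting nimpute=1 at stage 2 is right only if the call runs separately within each of the 20 stage 1 datasets. Run by treatment alone, it treats the 20 copies of each subject as 20 different subjects. The regression coefficients and residual variance are then drawn once per arm, with a precision that belongs to a sample 20 times larger, and the same draw is used in every copy. Rubin's rules rely on the spread between imputations to carry parameter uncertainty, and most of that part is lost for the monotone step.

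The affected dataset supplies the primary endpoint and the secondary endpoint of at least 4 points. The stage-specific SEs also determine the two Z values in the CHW formula. Text and code thus give two definitions of the primary p-value.

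**Working it through.** **Inputs from the documents.** Twenty imputations (SAP 8.2.2; protocol 15.0). 175 per arm, with an interim at about 50% (SAP 2.6), so 175/2, or about 87, per arm per stage. SAP 8.2.2 runs the MI separately for interim and post-interim subjects. Response rates 30% and 50% (SAP 2.6). Two-sided 5% level (SAP 8.1.3).

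**Count of parameter draws.** Draws = BY groups × nimpute.
- Stage 1: 2 arms × 20 = 40, or 20 per arm. This matches the specified number.
- Stage 2 as printed: 2 arms × 1 = 2, or **1 per arm**.
- Stage 2 with `_Imputation_` in BY: (2 × 20) groups × 1 = 40, or 20 per arm.

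The specified twenty is therefore not reproduced by the printed stage 2 call.

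**What that one draw is based on.** 20 × 175 = 3,500 rows per arm, or 20 × 87 = 1,740 per arm when run by stage. Stacking 20 copies multiplies X'X by 20, so the variance of the coefficient draw is about 1/20 of its proper value. Because all copies share the draw, it adds nothing to the spread between them.

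**Effect on the SE.** Rubin's total variance is T = Ū + (1 + 1/20)B, where B is the between-imputation variance. Trials were simulated with 12 autocorrelated weekly scores, baseline above 4, two binary covariates, monotone dropout, no intermittent gaps and imputations bounded at 0 and 10. The logistic model was that of SAP 8.2.2, with M = 20. There were about 1,200 trials per scenario at 87 per arm and 800 at 175 per arm. Dropout rates and the correlation of the scores are assumptions. The ratios are printed code to specified method:

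| Assumed dropout | B, 87/arm | SE, 87/arm | B, 175/arm | SE, 175/arm |
|---|---|---|---|---|
| 5%, weeks 2–12 | 0.854 | 0.998 | 0.924 | 0.999 |
| 15%, weeks 2–12 | 0.823 | 0.993 | 0.873 | 0.995 |
| 25%, weeks 2–12 | 0.779 | 0.986 | 0.833 | 0.989 |
| 35%, weeks 2–12 | 0.697 | 0.971 | 0.798 | 0.982 |
| 35%, all in weeks 1–3 | 0.736 | 0.966 | – | – |

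Percentages quoted elsewhere come from the ratios before rounding, so 0.986 appears as 1.5%. The 175-per-arm columns apply if the code is read without the stage split. Three smaller simulations of the same comparison, at 10% to 25% dropout and 87 per arm, gave SEs 0.3% to 2.1% too small.

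**Effect on a borderline p-value (87 per arm).** If the printed code gives Z = 1.96 (p = 0.050), the specified method gives p = 2 × [1 − Φ(1.96 × SE ratio)]. That is 0.052 at 15% dropout and 0.053 at 25%.

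**Effect on the error rate.** About 4,000 null trials per scenario (30% vs 30%) were paired into about 2,000 two-stage CHW tests with equal weights. The Monte Carlo SE of each rate is about √(0.05 × 0.95/2000) = 0.005.

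| Dropout | Specified | Printed |
|---|---|---|
| 15% | 0.0440 | 0.0455 |
| 25% | 0.0400 | 0.0445 |
| 35%, early | 0.0270 | 0.0420 |

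The ratio of the printed SE to its own sampling SD was 1.01 to 1.02 under the null and 0.99 to 1.11 across all scenarios.

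**If the labels do not survive.** Everything above keeps the 20 copies distinguishable. The documents do not say what the second call does to `_Imputation_`. If it numbered every row 1, MIANALYZE would have no separate datasets to combine. A single logistic model on the stacked rows would have an SE about 0.20 to 0.21 of the correct one (compare 1/√20 = 0.22 from the row count alone).

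**The case against.** The best defence is that the plan specifies the method fully and correctly in SAP 8.2.2, and that SAP 14 is headed as sample code. The listing is plainly a fragment. It omits the interim split, the reset step, the responder derivation, PROC LOGISTIC and PROC MIANALYZE, so a programmer has to complete it and may well notice the omission. The 20 copies are also not identical, since stage 1 values and residuals differ. The numerical effect is small, and in the null simulations the printed code was nearer to 5% than the specified method, which was conservative. The largest figures rest on 35% dropout, for which the documents give no support.

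Most of this stands on size: no loss of error control or power has been shown. It does not remove the mismatch. The section's first sentence presents the listing as the code used for the primary dataset, and its two seeds are the first two in the pre-specified list in SAP 13. Imputing within treatment group explains why treatment is in the BY statement but not why imputation number is absent. The label assumption is a fair caveat, but if it fails the printed code does worse.

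**Conclusion.** The point holds. As printed, stage 2 makes one parameter draw per arm from a 20-fold stacked fit, which contradicts the twenty separately imputed datasets in SAP 8.2.2 and protocol 15.0. This is a coding error, not a flaw in the specified method.

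Its effect is small. At 87 per arm and 15% to 25% dropout, the SE of the log odds ratio is 0.7% to 1.5% too small, and at most 3.4% in the harshest scenario tried. Simulated rejection under the null stayed below 5%. The conclusion about the code needs no assumption. The size rests on assumed dropout, assumed correlation of weekly scores, and survival of the imputation labels. It is worth correcting because the primary p-value should have one definition and a result near 0.05 could change sides.

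**What to change.** In stage 2, replace the BY statement with `by trt01pn _Imputation_;`, sort OUTDATA1 to match if needed, and keep nimpute=1. Each of the 20 datasets then gets its own parameter draw and keeps its label for MIANALYZE. The programs for the stage-specific runs, the sensitivity analyses and the 5-D Itch and Skindex-10 imputations are not printed, so check that they do the same.

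The cost is one variable and perhaps one sort. The SE returns to that of the specified method. In simulation at 30% vs 50% response and 25% dropout, two-stage CHW power was 95.5% with the correction and 96.5% as printed.
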